7.1. Viability and event-free survival

A Cox proportional hazards model will be used to assess the relationship between the number of viable myocardial segments (treated as a linear effect) and the primary outcome. Multivariable Cox analyses will be used to adjust the analysis for factors including age, sex, previous hospitalisation for heart failure, presence of diabetes, ejection fraction, extent of coronary disease, presence of chronic renal failure and modality of viability testing. The interaction between viability and treatment assignment on event-free survival will then be assessed using a Cox proportional hazards model containing the following covariates: viability (treated as a linear effect), randomly assigned treatment, and their interaction, plus the aforementioned list of baseline risk factors. In secondary analyses, the extent of viability will be divided into tertiles and Kaplan-Meier curves stratified by both viability tertile and treatment assignment presented. A sensitivity analysis will be performed where viability is defined irrespective of resting dysfunction (including segments with normal function at rest and with \$25% scar on CMR or contractile reserve on DSE).

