2.2. Hibernating Myocardium

The concept of viable but dysfunctional myocardium emerged approximately three decades ago, when it was observed that patients undergoing coronary artery bypass surgery for chronic stable angina had improvement or normalisation of left ventricular function following revascularisation(5). The energy utilized during myocyte contraction far exceeds the requirement for sustaining viability and, as such, myocardial tissue may survive in a hypocontractile state in the presence of reduced coronary blood flow or decreased coronary flow reserve, known as hibernation(6). Improvement of blood flow by revascularisation of hibernating myocardium can lead to restoration of regional and global left ventricular function and reversal of adverse remodelling(7-9), provided this is achieved before the onset of irreversible cellular and ultrastructural alterations(10). Potentially reversible, dysfunctional myocardium is characterised by preserved cellular integrity and a degree of contractile reserve, whereas scarring and absence of inducible contraction tend to reflect irreversible myocardial damage. Each of these distinguishing features can be used to predict myocardial viability or the likelihood of functional recovery following revascularisation. The parameter most widely used to determine viability is contractile reserve, which is assessed by measuring the augmentation of function of hypocontractile myocardium, in response to inotropic stimulation. The most commonly used agent is Dobutamine (at doses up to 20 µg/kg/min) while the change in regional and global contractility could be imaged by dobutamine stress echocardiography (DSE) or cine-magnetic resonance imaging (MRI). While MRI allows scar imaging as well as assessment of contractile reserve, at present it is contraindicated in patients with implantable cardioverter defibrillators or pacemakers in situ, which can limit its use in a heart failure population.

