4.1. Sample size

In REVIVED-BCIS2 all patients underwent viability imaging prior to randomisation; at least four viable segments which could be revascularised by PCI were required for inclusion. Of the 700 patients enrolled, viability was assessed with CMR in 491 and DSE in 187. Primary outcome data are available for 99.1% of patients. Serial echocardiographic data are available for a subset of these patients.

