5.2. CMR - segmental scar transmurality

Segmental scar transmurality is assessed visually on an ordinal scale as 0%, 1-25%, 26-50%, 51-75% and 76-100% of the segmental extent LGE. For trial inclusion, viability was adjudicated according to local protocols, with a recommendation that dysfunctional segments with \leq 25% transmurality be considered viable, \geq 50% non-viable and 25-50% based on local expert opinion. For core-laboratory adjudication, segmental viability was defined as a scar transmurality \leq 25% in a segment which is dysfunctional at rest[2,7,8]. Sensitivity analyses will also be performed using a cut-off of \leq 50%.

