5.3. DSE – contractile reserve

Viability is defined as the presence of contractile reserve in a segment which is dysfunctional at rest. Contractile reserve is defined as an improvement in wall motion score ≥ 1 grade (or ≥ 2 grades in segments which are dyskinetic at rest) during dobutamine stress, compared to baseline.

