5.4. Patients with CMR and DSE data

Where participants underwent both CMR and DSE data prior to randomisation, both scans are available and both are interpretable, the CMR data will be used in all analyses.

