6.3. Comparison of CMR and DSE as viability tests

An exploratory analysis will be used to compare patients who underwent viability testing with DSE and CMR, as well as sensitivity analyses restricted to each modality, for the key outcomes above. Demographic details will be displayed for the two groups as either frequency and percentage, mean \pm standard deviation or median (and inter-quartile range) depending on the type of data and normality of distribution. All Cox models concerning myocardial viability will be adjusted for the testing modality used.

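### The viability-by-treatment models pool CMR and DSE segment counts with modality only as a main effect, so a difference between tests can leak into the interaction and the tertile curves

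*Protocol*

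**What the plan says.** All references are to the REVIVED Viability Study SAP unless stated.

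- **Two definitions.** Section 5.2, for CMR: "For core-laboratory adjudication, segmental viability was defined as a scar transmurality" of 25% or less where the segment is dysfunctional at rest. Section 5.3, for DSE: "Viability is defined as the presence of contractile reserve in a segment which is dysfunctional at rest".
- **Both tests done.** Section 5.4: where "both scans are available and both are interpretable, the CMR data will be used in all analyses". No calibration of one count to the other is described.
- **Numbers.** Section 4.1: "Of the 700 patients enrolled, viability was assessed with CMR in 491 and DSE in 187".
- **Interaction model.** Section 7.1 specifies "viability (treated as a linear effect), randomly assigned treatment, and their interaction, plus the aforementioned list of baseline risk factors". That list includes testing modality. Section 7.2 repeats the scheme for recovery of ejection fraction.
- **Tertiles.** In both sections, as a secondary analysis, "the extent of viability will be divided into tertiles and Kaplan-Meier curves stratified by both viability tertile and treatment assignment presented".
- **Safeguards.** Section 6.3: "All Cox models concerning myocardial viability will be adjusted for the testing modality used". It also plans sensitivity analyses restricted to each modality, and section 9.1 (Appendix 2) plans a DSE-only repeat of the main viability analysis.

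**The concern.** Little scar and a response to dobutamine are different properties, so a given count need not mean the same on the two tests. A main effect for modality absorbs a difference in baseline hazard between the test groups. It does not absorb a difference in the effect of PCI between them. If modality is correlated with the count, the one available interaction term picks up part of that difference.

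Test choice was not random. Protocol section 2.2 says of MRI that "at present it is contraindicated in patients with implantable cardioverter defibrillators or pacemakers in situ", and device status is not among the adjustment factors named in section 7.1. The two test groups may therefore differ in ways that matter for treatment effect, although the documents give no evidence that they do.

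What is at stake is the study's primary objective (section 3.1.1): whether the extent of viability predicts the effect of PCI. The tertile curves carry no modality adjustment at all, so a contrast between tertiles can partly be a contrast between tests.

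**Working it through.** The plan states no figure of its own on this point, so there is none to reproduce.

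**Inputs from the documents.** 491 CMR and 187 DSE. Taking the two groups as not overlapping, the DSE share is p = 187/678 = 0.276 and p(1-p) = 0.200. Because CMR takes precedence when both exist, 187 is an upper limit for DSE counts in the pooled analysis.

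**Assumptions, because no count distribution is given.** Counts on 0-16 segments; within-test SD s of 3 or 3.5; DSE-minus-CMR mean offset d, varied.

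**1. Leakage into the interaction.** With 1:1 randomisation, the omitted modality x treatment term is orthogonal to the baseline main effects, so having modality as a main effect does not help. To first order:

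bias per segment = g x cov(count, modality)/var(count) = g x p(1-p)d / [s² + p(1-p)d²]

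where g is the modality-by-treatment log hazard ratio. If d = 0 or g = 0, the bias is zero.

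Two-segment offset, s = 3, ratio 1.35 (g = ln 1.35 = 0.30):
- cov = 0.200 x 2 = 0.40; var = 9 + 0.200 x 4 = 9.80; size of bias = 0.30 x 0.40/9.80 = 0.0122.
- SE = 1/√(events/4 x var). With an assumed 255 events, SE = 1/√(63.75 x 9.80) = 0.040, so bias/SE = 0.31.
- With the protocol's 300 events scaled to 678 of 700 patients (291), SE = 0.037 and bias/SE = 0.33.
- A bias of about 0.3 SE moves a two-sided 5% test to about 6%.

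**2. Check by Cox simulation.** Offset -3, s = 3.5, no true viability interaction, 300 runs per scenario. Estimates are per 3.5 segments.

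| Scenario | Planned model: estimate, rejection | With modality x treatment: estimate, rejection |
|---|---|---|
| d = 0, g = 0 | 0.001, 5.7% | 0.001, 5.3% |
| d = -3, g = 0 | -0.004, 5.7% | -0.003, 5.0% |
| d = -3, g = 0.4 | -0.067, 9.0% | -0.002, 4.3% |

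The formula gives 0.4 x 0.60/14.05 x 3.5 = 0.060 in size for the last row, close to the simulated 0.067. Monte Carlo error is about 1.3 points at 5% and 1.7 points at 9%. Simulated events were about 330-360, somewhat above 300. The second model also centred counts within modality. Once modality and modality x treatment are both in the model, centring does not change the viability-by-treatment coefficient, so the added term is what matters.

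**3. A true viability interaction.** Suppose the interaction acts on the count relative to each test's own mean, with coefficient b. Written in raw counts, the omitted modality x treatment coefficient is -b x d. By the formula in step 1, the estimate is then shrunk by the fraction p(1-p)d²/var(count), which is the share of count variance explained by modality. In simulated counts (s = 3.5) that share is about 6%, 12% and 20% for offsets of 2, 3 and 4 segments. This is a first-order result; no Cox simulation with a true interaction is available.

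**4. DSE share in pooled tertiles** (s = 3.5, CMR mean 7, 400 repeats):

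| Offset | Low | Middle | High |
|---|---|---|---|
| 0 | 27% | 28% | 28% |
| -1 | 34% | 27% | 21% |
| -2 | 40% | 26% | 16% |
| -3 | 47% | 25% | 12% |
| -4 | 53% | 22% | 8% |
| +2 | 16% | 26% | 40% |
| +4 | 8% | 22% | 53% |

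Tertiles cut within modality would hold the share near 27.6% throughout.

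**5. Where the plan itself moves the offset.** The 50% scar cut-off in section 5.2 can only raise CMR counts and leaves DSE counts alone. The section 7.1 sensitivity analysis that ignores resting dysfunction adds normal segments with little scar on CMR. A normal segment already has the best score (section 5.1), so it cannot improve by a grade on DSE.

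**The case against.** The strongest reply is that the plan already deals with modality. It is a covariate in the lead Cox models and, through the section 7.1 list, in the section 7.2 mixed model. Single-modality sensitivity analyses are prespecified. The CMR-only run has up to 491 patients and no mixing at all, and a DSE-only repeat is planned. The tertile curves are labelled secondary. Modality is fixed before randomisation, so PCI versus OMT within any tertile remains a randomised comparison. The trial itself uses one threshold, at least four viable segments, whatever the test. Finally, cutting tertiles within modality would erase a real difference if DSE patients truly have less viable myocardium, and would put patients with equal counts in different tertiles.

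Much of this stands. The safeguards would expose a problem, the curves are not the lead analysis, and within-modality tertiles should not replace the pooled ones. What it does not answer is the pooled interaction: a main effect cannot carry a treatment effect that differs by modality, and a sensitivity run does not correct the lead estimate.

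A reader might go further and infer that the tertiles do sort patients by test. The documents give no count distribution, and with no offset there is no sorting. A reader might also infer that an offset alone creates a false interaction. It does not: rejection stayed near 5% with a 3-segment offset and no modality-by-treatment effect. Nor do the documents support a figure for a spurious hazard ratio between bottom and top tertiles. That would need an assumed excess hazard in DSE patients and an unadjusted tertile contrast that the SAP does not plan.

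**Conclusion.** The point holds as a conditional weakness in the specification. Two non-equivalent counts share one linear term and one viability-by-treatment term, with modality only as a main effect. A false interaction requires both an offset between the tests and a treatment effect that differs by modality. Shrinkage of a true interaction requires an offset when the effect acts on the count within each test. The documents establish neither condition, so the size is a range: nil at zero offset; about 0.3 SE for 2 segments and a ratio of 1.35; about 9% rejection in place of 5% for 3 segments and a log hazard ratio of 0.4. The secondary tertile curves can partly reflect test type, to a degree that depends on the same unknown offset. Priority is minor: the change is cheap and protects the term that answers the primary objective.

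**What to change.** In sections 7.1 and 7.2, add modality x treatment to every viability-by-treatment model, or equivalently estimate the interaction within each modality and combine the two. The raw count can stay as the viability variable. Show the tertile Kaplan-Meier curves with tertiles cut within modality alongside the pooled tertiles, and report the tertile limits and the share of each modality per tertile. Keep the single-modality analyses as planned.

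The cost is one extra model term with slightly wider intervals, and test-specific tertile limits that must be displayed. No new data are needed.

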5.1. Wall motion scoring

For CMR and DSE, wall motion score will be classified on a five-point ordinal Likert scale as 1 – normal, 2 – hypokinetic, 3 – akinetic, 4 – dyskinetic, 5 – aneurysmal. For GSTT echocardiography core laboratory (non-DSE) measurements, the latter two points are combined into one category.

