7.2. Viability and improvement in left ventricular ejection fraction

A Cox proportional hazards model will be used to assess the relationship between the number of viable myocardial segments (treated as a linear effect) and recovery of left ventricular function at six and twelve months. Multivariable Cox analyses will be used to adjust the analysis for the list of baseline factors in section 7.1. The interaction between viability and treatment assignment on improvement in left ventricular function will then be assessed using a Cox proportional hazards model containing the following co-variates: viability (treated as a linear effect), randomly assigned treatment, and their interaction, plus the aforementioned list of baseline risk factors. In secondary analyses, the extent of viability will be divided into tertiles and Kaplan-Meier curves stratified by both viability tertile and treatment assignment presented. A sensitivity analysis will be performed where viability is defined irrespective of resting dysfunction (including segments with normal function at rest and with $\leq 25\%$ scar on CMR or contractile reserve on DSE).

The relationship between the number of viable segments and recovery of left ventricular function will also be assessed using the change in ejection fraction at 6 and 12 months with a linear mixed effects model for repeated measures adjusting for the variables specified in section 7.1⁷. This model accounts for the baseline ejection fraction, while also incorporating both follow-up measurements, and enables the inclusion of participants with missing measurements. The mean change in ejection fraction at each timepoint along with the association between viability and these means will be estimated. The model includes a variable for time, viability, and an interaction between time and viability, and assumes no effect of treatment at baseline. An unstructured variance-covariance matrix will be used to allow for correlations between repeated measures of ejection fraction. The model will be fitted using restricted maximum likelihood and assumes that missing ejection fraction values are missing-at-random.

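### The viability sensitivity analysis that drops the resting-dysfunction condition can change counts only in CMR patients, because a normal segment cannot show contractile reserve on DSE

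*Protocol*

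**What the plan says.** The Viability Study SAP counts viable segments per patient and enters the count as a linear term. In the primary definition a segment must be dysfunctional at rest. It must then show scar of at most 25% on CMR (section 5.2) or contractile reserve on DSE (section 5.3).

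Sections 7.1 (event-free survival) and 7.2 (LVEF improvement) each add a check on that definition: "A sensitivity analysis will be performed where viability is defined irrespective of resting dysfunction (including segments with normal function at rest". The criterion for DSE in the same parenthesis is still "or contractile reserve on DSE".

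Two definitions settle what that means:

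- Section 5.1, for CMR and DSE: "wall motion score will be classified on a five-point ordinal Likert scale as 1 – normal, 2 – hypokinetic", and onwards to aneurysmal at grade 5.
- Section 5.3: "Contractile reserve is defined as an improvement in wall motion score ≥ 1 grade", or two grades if the segment is dyskinetic at rest, compared with baseline.

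Section 6.3 adjusts all viability Cox models for modality and plans sensitivity analyses restricted to each modality. Section 5.4 gives CMR precedence where a patient has both tests.

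**The concern.** The check is meant to show whether the result depends on leaving normally contracting myocardium out of the count. On CMR it can do that, because scar is read independently of wall motion. On DSE the remaining criterion is itself an improvement in wall motion, and a normal segment has no better grade to move to. The relaxation would then operate in one modality and be void in the other.

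Two consequences follow. In the pooled model, an extra viable segment could be normal myocardium in a CMR patient but never in a DSE patient, and the viability-by-treatment interaction would be estimated on that mixed scale. In a DSE-only run, the analysis would return the main DSE result unchanged, and the agreement could be read as robustness although nothing had been varied.

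**Working it through.** The plan states no figure on this point, so there is none to reproduce. The check is logical, followed by an illustration of size.

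**1. Can a normal segment show reserve?** Inputs: the scale in section 5.1 and the rule in section 5.3. The largest possible improvement from resting grade r is r − 1.

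| Resting grade | Largest improvement | Required | Reserve possible? |
|---|---|---|---|
| 1 normal | 0 | 1 | No |
| 2 hypokinetic | 1 | 1 | Yes |
| 3 akinetic | 2 | 1 | Yes |
| 4 dyskinetic | 3 | 2 | Yes |
| 5 aneurysmal | 4 | 1 | Yes |

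Only the normal segment fails, and it always fails. Every DSE segment that can qualify is already dysfunctional at rest, so a DSE patient's sensitivity count equals the primary count. The scale in section 11 of the main protocol also has no grade better than normal.

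**2. Who is affected?** Section 4.1 gives CMR in 491 patients and DSE in 187: 187 / (491 + 187) = 187 / 678 = 27.6%. This is an upper limit. Patients with both interpretable tests are analysed on CMR (section 5.4), and unusable studies are excluded (section 6.4).

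**3. How large is the gap?** The documents do not say how many segments were normal at rest. Assume 16 segments (section 4.2 excludes segment 17), the same hearts in both modalities, and 95% of normal segments with scar of at most 25%. The 95% and the normal shares below are assumptions.

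Gap in mean count = 16 × 0.95 × share of segments normal at rest

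- 5% normal: 16 × 0.95 × 0.05 = 0.76, about 0.8 segments
- 10% normal: 16 × 0.95 × 0.10 = 1.52, about 1.5 segments
- 25% normal: 16 × 0.95 × 0.25 = 3.80 segments

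**4. Does adjustment for modality repair it?** Write V for the primary count, N for the number of normal low-scar segments, M = 1 for CMR and 0 for DSE, and T for treatment. The sensitivity count is C = V + M·N. With n the mean of N:

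- Main effect: M·N = n·M + M·(N − n). The modality covariate absorbs the average shift n·M.
- Interaction: C·T = V·T + n·M·T + M·(N − n)·T. The middle term is a treatment-by-modality contrast. The SAP specifies no treatment-by-modality term, so the average shift is not absorbed here.

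The covariate therefore deals with the average shift in the main effect, but not in the interaction that the analysis is meant to check.

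**The case against.** **The parenthesis can be read differently.** It might list two classes: all normal segments, and separately any segment with little scar or with reserve. Normal DSE segments would then count. This fits the stated aim, but it is the less natural grammar, and it would need the same clarifying sentence before anyone could program it.

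**The two modalities already differ.** The primary definition pools low scar on CMR with contractile reserve on DSE, and the SAP answers with the covariate and the modality-restricted analyses of section 6.3. That stands: non-equivalence between tests is not new here. What is new is a change of definition that reaches only one of them. The restricted analyses help on the CMR side, where the relaxed definition is coherent. Section 6.3 does not say that they are crossed with this definition. On the DSE side, such a run would repeat the main DSE result.

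**Tertiles.** A reader might infer that the viability tertiles will sort patients partly by modality. The text does not support this. In both sections the tertiles belong to the secondary analyses, and nothing says that they are re-formed on the sensitivity count. They are affected only if that is done.

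**Scope.** A reader might also infer that the primary viability test is compromised. It is not: the fault is confined to one sensitivity analysis, stated twice, in a sub-study plan.

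**Conclusion.** The point holds in limited form. On the SAP's own definitions and the natural reading of sections 7.1 and 7.2, no normal-at-rest DSE segment can enter the relaxed count. The analysis therefore varies the definition in CMR patients only and leaves up to 27.6% of the pooled patients as they were. This part needs no assumption beyond that reading.

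The numerical effect is uncertain: about 0.8 to 3.8 segments between modalities for a normal share of 5% to 25%, under the assumptions shown. How far this would move the estimated interaction cannot be determined from the documents. The primary viability model and the main trial results do not change. It is a stated rule that defeats its own purpose, not a detail left open, and it should be corrected.

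**What to change.** Either of these, written into both 7.1 and 7.2:

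1. Run this sensitivity analysis in CMR patients only and label it so. This is the cleaner option, because the relaxed definition is coherent there.
2. State that, in this analysis, DSE segments normal at rest (grade 1) count as viable without a reserve requirement, keep the reserve rule for dysfunctional segments, and report results by modality.

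The second option has a small drawback: normal DSE segments would carry no scar check while normal CMR segments would. Under the assumptions above, the remaining gap is 16 × 0.05 × share, which is 0.04, 0.08 or 0.20 segments at 5%, 10% or 25% normal.

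If tertiles are to be formed for this analysis, the text should say so and name the count used. The cost is one sentence in each section. Resting wall motion must already be scored to judge reserve, so no re-reading of scans is needed.
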